2.4.1.1 Non-nodal lesions

Following treatment, lesions may have longest diameter measurements smaller than the image reconstruction interval. Lesions smaller than twice the reconstruction interval are subject to substantial "partial volume" effects (i.e., size may be underestimated because of the distance of the cut from the longest diameter; such lesions may appear to have responded or progressed on subsequent examinations, when, in fact, they remain the same size).

If the lesion has completely disappeared, the lesion size should be reported as 0 mm.

Measurements of non-nodal target lesions that become 5 mm or less in longest diameter are likely to be non-reproducible. Therefore, it is recommended to report a default value of 5 mm, instead of the actual measurement. This default value is derived from the 5 mm CT slice thickness (but should not be changed with varying CT slice thickness). Actual measurement should be given for all lesions larger than 5 mm in longest diameter irrespective of slice thickness/reconstruction interval.

In other cases where the lesion cannot be reliably measured for reasons other than its size (e.g., borders of the lesion are confounded by neighboring anatomical structures), no measurement should be entered and the lesion cannot be evaluated.

2.4.1.2 Nodal lesions

A nodal lesion less than 10 mm in size by short axis is considered normal. Lymph nodes are not expected to disappear completely, so a "non-zero size" will always persist.

Measurements of nodal target lesions that become 5 mm or less in short axis are likely to be non-reproducible. Therefore, it is recommended to report a default value of 5 mm, instead of the actual measurement. This default value is derived from the 5 mm CT slice thickness (but should not be changed with varying CT slice thickness). Actual measurement should be given for all lesions larger than 5 mm in short axis irrespective of slice thickness/reconstruction interval.

However, once a target nodal lesion shrinks to less than 10 mm in its short axis, it will be considered normal for response purpose determination. The lymph node measurements will continue to be recorded to allow the values to be included in the sum of diameters for target lesions, which may be required subsequently for response determination.

2.4.2 Determination of target lesion response

Table 2-1 Response criteria for target lesions

Response Criteria	Evaluation of target lesions
Complete Response (CR):	Disappearance of all non-nodal target lesions. In addition, any pathological lymph nodes assigned as target lesions must have a reduction in short axis to $< 10 \text{ mm}^{-1}$
Partial Response (PR):	At least a 30% decrease in the sum of diameter of all target lesions, taking as reference the baseline sum of diameters.
Progressive Disease (PD):	At least a 20% increase in the sum of diameter of all measured target lesions, taking as reference the smallest sum of diameter of all target lesions recorded at or after baseline. In addition to the relative increase of 20%, the sum must also demonstrate an absolute increase of at least 5 mm ² .
Stable Disease (SD):	Neither sufficient shrinkage to qualify for PR or CR nor an increase in lesions which would qualify for PD.
Unknown (UNK)	Progression has not been documented and one or more target lesions have not been assessed or have been assessed using a different method than baseline. ³

^{1.} SOD for CR may not be zero when nodal lesions are part of target lesions

Notes on target lesion response

Reappearance of lesions: If the lesion appears at the same anatomical location where a target lesion had previously disappeared, it is advised that the time point of lesion disappearance (i.e., the "0 mm" recording) be re-evaluated to make sure that the lesion was not actually present and/or not visualized for technical reasons in this previous assessment. If it is not possible to change the 0 value, then the investigator/radiologist has to decide between the following possibilities:

². Following an initial CR, a PD cannot be assigned if all non-nodal target lesions are still not present and all nodal lesions are <10 mm in size. In this case, the target lesion response is CR

³. In exceptional circumstances an UNK response due to change in method could be over-ruled by the investigator or central reviewer using expert judgment based on the available information (see Notes on target lesion response and methodology change in Section 2.2).

- The lesion is a new lesion, in which case the overall tumor assessment will be considered as progressive disease
- The lesion is clearly a reappearance of a previously disappeared lesion, in which case the size of the lesion has to be entered in the eCRF and the tumor assessment will remain based on the sum of tumor measurements as presented in Table 2-1 above (i.e., a PD will be determined if there is at least 20% increase in the sum of diameters of all measured target lesions, taking as reference the smallest sum of diameters of all target lesions recorded at or after baseline with at least 5 mm increase in the absolute sum of the diameters). Proper documentation should be available to support this decision. This applies to patients who have not achieved target response of CR. For patients who have achieved CR, please refer to last bullet in this section.
- For those patients who have only one target lesion at baseline, the reappearance of the target lesion which disappeared previously, even if still small, is considered a PD.
- Missing measurements: In cases where measurements are missing for one or more target lesions it is sometimes still possible to assign PD based on the measurements of the remaining lesions. For example, if the sum of diameters for 5 target lesions at baseline is 100 mm at baseline and the sum of diameters for 3 of those lesions at a post-baseline visit is 140 mm (with data for 2 other lesions missing) then a PD should be assigned. However, in other cases where a PD cannot definitely be attributed, the target lesion response would be UNK.
- Nodal lesion decrease to normal size: When nodal disease is included in the sum of target lesions and the nodes decrease to "normal" size they should still have a measurement recorded on scans. This measurement should be reported even when the nodes are normal in order not to overstate progression should it be based on increase in the size of nodes.
- Lesions split: In some circumstances, disease that is measurable as a target lesion at baseline and appears to be one mass can split to become two or more smaller sub-lesions. When this occurs, the diameters (long axis non-nodal lesion, short axis nodal lesions) of the two split lesions should be added together and the sum recorded in the diameter field on the case report form under the original lesion number. This value will be included in the sum of diameters when deriving target lesion response. The individual split lesions will not be considered as new lesions, and will not automatically trigger a PD designation.
- Lesions coalesced: Conversely, it is also possible that two or more lesions which were distinctly separate at baseline become confluent at subsequent visits. When this occurs a plane between the original lesions may be maintained that would aid in obtaining diameter measurements of each individual lesion. If the lesions have truly coalesced such that they are no longer separable, the maximal diameters (long axis non-nodal lesion, short axis nodal lesions) of the "merged lesion" should be used when calculating the sum of diameters for target lesions. On the case report form, the diameter of the "merged lesion" should be recorded for the size of one of the original lesions while a size of "0"mm should be entered for the remaining lesion numbers which have coalesced.
- The **measurements for nodal lesions**, even if less than 10 mm in size, will contribute to the calculation of target lesion response in the usual way with slight modifications.

- Since lesions less than 10 mm are considered normal, a CR for target lesion response should be assigned when all nodal target lesions shrink to less than 10 mm and all non-nodal target lesions have disappeared.
- Once a CR target lesion response has been assigned a CR will continue to be appropriate (in the absence of missing data) until progression of target lesions.
- Following a CR, a PD can subsequently only be assigned for target lesion response if either a non-nodal target lesion "reappears" or if any single nodal lesion is at least 10 mm and there is at least 20% increase in sum of the diameters of all nodal target lesions relative to nadir with at least 5 mm increase in the absolute sum of the diameters
- A change in method for the evaluation of one or more lesions will usually lead to an UNK target lesion response unless there is progression indicated by the remaining lesions which have been evaluated by the same method. In exceptional circumstances an investigator or central reviewer might over-rule this assignment to put a non-UNK response using expert judgment based on the available information. E.g. a change to a more sensitive method might indicate some tumor shrinkage of target lesions and definitely rule out progression in which case the investigator might assign an SD target lesion response; however, this should be done with caution and conservatively as the response categories have well defined criteria.

2.4.3 Determination of non-target lesion response

Table 2-2 Response criteria for non-target lesions

Response Criteria	Evaluation of non-target lesions Disappearance of all non-target lesions. In addition, all lymph nodes assigned a non-target lesions must be non-pathological in size (< 10 mm short axis)		
Complete Response (CR):			
Progressive Disease (PD):	Unequivocal progression of existing non-target lesions. ¹		
Non-CR/Non-PD:	Neither CR nor PD		
Unknown (UNK)	Progression has not been documented and one or more non-target lesions have not been assessed or have been assessed using a different method than baseline ²		

The assignment of PD solely based on change in non-target lesions in light of target lesion response of CR, PR or SD should be exceptional. In such circumstances, the opinion of the investigator or central reviewer does prevail. It is recommended that the investigator and/or central reviewer should use expert judgement to assign a Non-UNK response wherever possible (see notes section for more details)

Notes on non-target lesion response

• The investigator and/or central reviewer can use expert judgment to assign a non-UNK response wherever possible, even where lesions have not been fully assessed or a different method has been used. In many of these situations it may still be possible to identify equivocal progression (PD) or definitively rule this out (non-CR/Non-PD) based on the available information. In the specific case where a more sensitive method has been used indicating the absence of any non-target lesions, a CR response can also be assigned.

- The response for non-target lesions is **CR** only if all non-target non-nodal lesions which were evaluated at baseline are now all absent and with all non-target nodal lesions returned to normal size (i.e. < 10 mm). If any of the non-target lesions are still present, or there are any abnormal nodal lesions (i.e. ≥ 10 mm) the response can only be '**Non-CR/Non-PD**' unless there is unequivocal progression of the non-target lesions (in which case response is **PD**) or it is not possible to determine whether there is unequivocal progression (in which case response is UNK).
- Unequivocal progression: To achieve "unequivocal progression" on the basis of non-target disease there must be an overall level of substantial worsening in non-target disease such that, even in presence of CR, PR or SD in target disease, the overall tumor burden has increased sufficiently to merit discontinuation of therapy. A modest "increase" in the size of one or more non-target lesions is usually not sufficient to qualify for unequivocal progression status. The designation of overall progression solely on the basis of change in non-target disease in the face of CR, PR or SD of target disease is therefore expected to be rare. In order for a PD to be assigned on the basis of non-target lesions, the increase in the extent of the disease must be substantial even in cases where there is no measurable disease at baseline. If there is unequivocal progression of non-target lesion(s), then at least one of the non-target lesions must be assigned a status of "Worsened". Where possible, similar rules to those described in Section 2.4.2 for assigning PD following a CR for the non-target lesion response in the presence of non-target lesions nodal lesions should be applied.

2.4.4 New lesions

The appearance of a new lesion is always associated with Progressive Disease (PD) and has to be recorded as a new lesion in the New Lesion eCRF page.

- If a new lesion is **equivocal**, for example because of its small size, continued therapy and follow-up evaluation will clarify if it represents truly new disease. If repeat scans confirm there is definitely a new lesion, then progression should be declared using the date of the first observation of the lesion
- If new disease is observed in a region which was **not scanned at baseline** or where the particular baseline scan is not available for some reason, then this should be considered as a PD. The one exception to this is when there are no baseline scans at all available for a patient in which case the response should be UNK, as for any of this patient's assessment (see Section 2.5).
- A **lymph node is considered as a "new lesion"** and, therefore, indicative of progressive disease if the short axis increases in size to ≥ 10 mm for the first time in the study plus 5 mm absolute increase.
 - **FDG-PET:** can complement CT scans in assessing progression (particularly possible for 'new' disease). See Section 2.2.

2.5 Evaluation of overall lesion response

The evaluation of overall lesion response at each assessment is a composite of the target lesion response, non-target lesion response and presence of new lesions as shown below in Table 2-3.

Table 2-3 Overall lesion response at each assessment

Target lesions	Non-target lesions	New Lesions	Overall lesion response
CR	CR	No	CR1
CR	Non-CR/Non-PD ³	No	PR
CR, PR, SD	UNK	No	UNK
PR	Non-PD and not UNK	No	PR ¹
SD	Non-PD and not UNK	No	SD ^{1, 2}
UNK	Non-PD or UNK	No	UNK ¹
PD	Any	Yes or No	PD
Any	PD	Yes or No	PD
Any	Any	Yes	PD

^{1.} This overall lesion response also applies when there are no non-target lesions identified at baseline.

If there are no baseline scans available at all, then the overall lesion response at each assessment should be considered Unknown (UNK).

In some circumstances it may be difficult to distinguish residual disease from normal tissue. When the evaluation of complete response depends on this determination, it is recommended that the residual lesion be investigated (fine needle aspirate/biopsy) to confirm the CR.

3 Efficacy definitions

The following definitions primarily relate to patients who have measurable disease at baseline. Section 3.2.9 outlines the special considerations that need to be given to patients with no measurable disease at baseline in order to apply the same concepts.

3.1 Best overall response

The best overall response is the best response recorded from the start of the treatment until disease progression/recurrence (taking as reference for PD the smallest measurements recorded since the treatment started). In general, the patient's best response assignment will depend on the achievement of both measurement and confirmation criteria.

The best overall response will usually be determined from response assessments undertaken while on treatment. However, if any assessments occur after treatment withdrawal the protocol should specifically describe if these will be included in the determination of best overall response and/or whether these additional assessments will be required for sensitivity or supportive analyses. As a default, any assessments taken more than 30 days after the last dose of study treatment will not be included in the best overall response derivation. If any alternative cancer therapy is taken while on study any subsequent assessments would ordinarily be excluded from the best overall response determination. If response assessments taken after withdrawal from study treatment and/or alternative therapy are to be included in the main endpoint determination, then this should be described and justified in the protocol.

Where a study requires confirmation of response (PR or CR), changes in tumor measurements must be confirmed by repeat assessments that should be performed not less than 4 weeks after the criteria for response are first met.

². Once confirmed PR was achieved, all these assessments are considered PR.

³. As defined in Section 2.4

Longer intervals may also be appropriate. However, this must be clearly stated in the protocol. The main goal of confirmation of objective response is to avoid overestimating the response rate observed. In cases where confirmation of response is not feasible, it should be made clear when reporting the outcome of such studies that the responses are not confirmed.

- For non-randomized trials where response is the primary endpoint, confirmation is needed.
- -For trials intended to support accelerated approval, confirmation is needed
- For all other trials, confirmation of response may be considered optional.

The best overall response for each patient is determined from the sequence of overall (lesion) responses according to the following rules:

- CR = at least two determinations of CR at least 4 weeks apart before progression where confirmation required or one determination of CR prior to progression where confirmation not required
- PR = at least two determinations of PR or better at least 4 weeks apart before progression (and not qualifying for a CR) where confirmation required or one determination of PR prior to progression where confirmation not required
- SD = at least one SD assessment (or better) > 6 weeks after randomization/start of treatment (and not qualifying for CR or PR).

The protocol should state if randomization or start of treatment is used as start date (baseline). This is then used in all definitions.

If a different minimum follow-up period is required to classify for best overall response='stable disease', this must be specified in the protocol.

• PD = progression ≤ 12 weeks after randomization/ start of treatment (and not qualifying for CR, PR or SD).

If PD in a different follow-up period is considered to classify for best overall response='progressive disease', this must be specified in the protocol.

The protocol should state if discontinuation due to 'Disease progression' or death due to study indication is considered PD even if this was not accompanied by documentation of PD based on tumor measurements. This depends on Phase of the study and the primary endpoint (e.g. Phase III studies in which progression-free survival is primary endpoint should consider only documented PD, whereas Phase I and II studies may consider all clinical deteriorations PD). The following sentence therefore is only applicable if this is specified in the protocol:

Patients with symptoms of rapidly progressing disease without radiologic evidence will be classified as progression only when clear evidence of clinical deterioration is documented and/or patient discontinued due to 'Disease progression' or death due to study indication.

• UNK = all other cases (i.e. not qualifying for confirmed CR or PR and without SD after more than 6 weeks or early progression within the first 12 weeks)

The time durations specified in the SD/PD/UNK definitions above are defaults based on a 6 week tumor assessment frequency. However these may be modified for specific indications which are more or less aggressive. In addition, it is envisaged that the time duration may also take into account assessment windows. E.g. if the assessment occurs every 6 weeks with a time

Page 182

window of +/- 7 days, a BOR of SD would require a SD or better response longer than 5 weeks after randomization/start of treatment.

Overall lesion responses of CR must stay the same until progression sets in, with the exception of a UNK status. A patient who had a CR cannot subsequently have a lower status other than a PD, e.g. PR or SD, as this would imply a progression based on one or more lesions reappearing, in which case the status would become a PD.

Once an overall lesion response of PR is observed (which may have to be a confirmed PR depending on the study) this assignment must stay the same or improve over time until progression sets in, with the exception of an UNK status. However, in studies where confirmation of response is required, if a patient has a single PR (≥30% reduction of tumor burden compared to baseline) at one assessment, followed by a <30% reduction from baseline at the next assessment (but not $\geq 20\%$ increase from previous smallest sum), the objective status at that assessment should be SD. Once a confirmed PR was seen, the overall lesion response should be considered PR (or UNK) until progression is documented or the lesions totally disappear in which case a CR assignment is applicable. In studies where confirmation of response is not required after a single PR the overall lesion response should still be considered PR (or UNK) until progression is documented or the lesion totally disappears in which case a CR assignment is applicable.

Example: In a case where confirmation of response is required the sum of lesion diameters is 200 mm at baseline and then 140 mm - 150 mm - 140 mm - 160 mm - 160 mm at the subsequent visits. Assuming that non-target lesions did not progress, the overall lesion response would be PR - SD - PR - PR - PR. The second assessment with 140 mm confirms the PR for this patient. All subsequent assessments are considered PR even if tumor measurements decrease only by 20% compared to baseline (200 mm to 160 mm) at the following assessments.

If the patient progressed but continues study treatment, further assessments are not considered for the determination of best overall response.

Note: these cases may be described as a separate finding in the CSR but not included in the overall response or disease control rates.

The best overall response for a patient is always calculated, based on the sequence of overall lesion responses. However, the overall lesion response at a given assessment may be provided from different sources:

- Investigator overall lesion response
- Central Blinded Review overall lesion response
- Novartis calculated overall lesion response (based on measurements from either Investigator or Central Review)

The primary analysis of the best overall response will be based on the sequence of investigator/central blinded review/calculated (investigator)/calculated (central) overall lesion responses.

Specify which determination of best overall response will be considered primary (and delete the other terms in the text). If a central blinded review is used (e.g. in an open-label study in Amended Protocol Version 06 (Clean)

which response is the primary endpoint), the best overall response evaluated by the central blinded review will always be considered the primary response.

Based on the patients' best overall response during the study, the following rates are then calculated:

Overall response rate (ORR) is the proportion of patients with a best overall response of CR or PR. This is also referred to as 'Objective response rate' in some protocols or publications.

Disease control rate (DCR) is the proportion of patients with a best overall response of CR or PR or SD. The objective of this endpoint is to summarize patients with signs of "activity" defined as either shrinkage of tumor (regardless of duration) or slowing down of tumor growth.

Clinical benefit rate (CBR) is the proportion of patients with a best overall response of CR or PR, or an overall lesion response of SD or Non-CR/Non-PD which lasts for a minimum time duration (with a default of at least 24 weeks in breast cancer studies). This endpoint measures signs of activity taking into account duration of disease stabilization.

Another approach is to summarize the progression rate at a certain time point after baseline. In this case, the following definition is used:

Early progression rate (EPR) is the proportion of patients with progressive disease within 8 weeks of the start of treatment.

The protocol should define populations for which these will be calculated. The timepoint for EPR is study specific. EPR is used for the multinomial designs of Dent and Zee (2001) and counts all patients who at the specified assessment (in this example the assessment would be at 8 weeks \pm window) do not have an overall lesion response of SD, PR or CR. Patients with an unknown (UNK) assessment at that time point and no PD before, will not be counted as early progressors in the analysis but may be included in the denominator of the EPR rate, depending on the analysis population used. Similarly when examining overall response and disease control, patients with a best overall response assessment of unknown (UNK) will not be regarded as "responders" but may be included in the denominator for ORR and DCR calculation depending on the analysis population (e.g. populations based on an ITT approach).

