Any potentially measurable lesion that has been previously treated with radiotherapy should be considered as a non-measurable lesion. However, if a lesion previously treated with radiotherapy has clearly progressed since the radiotherapy, it can be considered as a measurable lesion.

Each lesion that is measured at baseline must be measured by the same method (either same radiologic/nuclear method or by physical exam) throughout the study so that the comparison is consistent. Criteria required for determining partial or complete response should be present for at least 4 weeks.

Chest x-rays and ultrasound should not be used to measure tumor lesions.

Core Phase Treatment phase imaging assessments

Imaging assessments as described in Table 7-3 should be performed using the same imaging modality used at screening, irrespective of study treatment interruption or actual dosing. Imaging assessments for response evaluation will be performed every 12 weeks (+/- 7 days) during the Core Phase. The 12 week interval should be followed regardless of whether study treatment is temporarily withheld or unscheduled assessments are performed.

Additional imaging assessments may be performed at any time during the study at the investigator's discretion to support the efficacy evaluations for a subject, as necessary. Clinical suspicion of disease progression at any time requires a physical examination and imaging assessments to be performed promptly rather than waiting for the next scheduled imaging assessment.

Each lesion that is measured at screening must be measured by the same method (either same imaging method or by photography, including a metric ruler) and when possible, the same local radiologist/physician throughout the study so that the comparison is consistent. If an off-schedule imaging assessment is performed because progression is suspected, subsequent imaging assessments should be performed in accordance with the original imaging schedule.

Combined Positron Emission Tomography/Computed Tomography (PET/CT) may be used only if the CT is of similar diagnostic quality as a CT performed without PET, including the utilization of IV contrast media. At the discretion of the Investigators, FDG-PET scans may be performed to document progressive disease per RECIST v1.1 (Appendix 5).

Extension Phase

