2.7.1 Secondary endpoints

The mFAS will be used for the secondary efficacy analyses.

Progression free survival

Secondary endpoints include PFS, defined as the time from the date of start of treatment to the date of the first documented progression or death due to any cause. PFS will be based on local investigators review of tumor assessments and using RECIST 1.1 criteria (see Appendix 5 of the study protocol). If a patient has not progressed or died at the analysis cut-off date, PFS will be censored at the date of the last adequate tumor evaluation date before the cut-off date. PFS events documented after the initiation of new anti-neoplastic therapy (i.e. RECIST 1.1 documented disease progression or death) will be considered for the primary analysis provided tumor assessments continue after initiation of new cancer therapy. Discontinuation due to disease progression (collected on the 'End of treatment' and 'End of post treatment follow up' disposition pages) without supporting objective evidence satisfying progression criteria per RECIST 1.1 will not be considered disease progression for PFS derivation. Clinical deterioration will not be considered as a qualifying event for progression.

Overall response rate

ORR is defined as the proportion of patients with best overall response (BOR) of complete response (CR) or partial response (PR) according to RECIST 1.1 (see Appendix 5 of the study protocol). ORR will be calculated based using local investigators review of tumor assessment data in patients with measurable disease at baseline. Patients with only non-measurable disease at baseline will be part of the analysis and will be included in the numerator only if a complete response was observed. Tumor assessments performed before the start of any further antineoplastic therapy (i.e. any additional secondary antineoplastic therapy or surgery) will be considered in the assessment of BOR.

Clinical benefit rate (CBR)

CBR is defined as the proportion of patients with a best overall response of CR or PR, or an overall lesion response of stable disease (SD) lasting 24 weeks or longer or Non-CR/ Non-PD lasting 24 weeks or longer, according to RECIST 1.1 criteria. A patient will be considered to have SD for 24 weeks or longer if a SD response is recorded at 23 weeks or later from

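### Best overall response keeps a 12-week limit for PD that was set for 6-week scans, so progression found at an in-window first scan after day 84 is classed as Unknown

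*Protocol*

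**What the plan says.** Protocol 10.5.1.3 defines ORR through BOR and refers to Appendix 5 for detail. SAP 2.7.1 does the same, defining ORR by "best overall response (BOR) of complete response (CR) or partial response (PR) according to RECIST 1.1 (see Appendix 5 of the study protocol".

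Appendix 5, section 3.1, assigns a BOR of PD for "progression ≤ 12 weeks after randomization/ start of treatment (and not qualifying for CR, PR or SD". The Unknown category takes every remaining case, meaning patients without a confirmed response and "without SD after more than 6 weeks or early progression within the first 12 weeks".

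The same section explains where the limits come from: "The time durations specified in the SD/PD/UNK definitions above are defaults based on a 6 week tumor assessment frequency". It sets a condition for departing from the PD limit: "If PD in a different follow-up period is considered to classify for best overall response='progressive disease', this must be specified in the protocol". It also says that "it is envisaged that the time duration may also take into account assessment windows". Its only worked example concerns SD: with 6-week scans and a 7-day window, "a BOR of SD would require a SD or better response longer than 5 weeks after randomization/start of treatment".

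Protocol 7.2.1.1 sets this trial's schedule: "Imaging assessments for response evaluation will be performed every 12 weeks (+/- 7 days) during the Core Phase". Table 7-3 also gives 12 weeks. Neither protocol 10.5.1 nor SAP 2.7.1 to 2.7.3 states another PD limit or applies the scan window to it.

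**The concern.** The PD limit and the first scheduled scan fall at the same time point, 12 weeks. The limit has no tolerance, while the scan has a week on either side. A patient can attend on time under the protocol, have RECIST progression documented at the first scan, and still be classed with patients whose response could not be assessed.

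In a non-comparative trial, PD and Unknown mean different things to a reader: one is treatment failure, the other is missing information. The rule would put some documented progressions under the second label.

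The SAP allows for the window in other places. The primary endpoint uses 24 weeks plus or minus 1 (SAP 2.5.3), CBR accepts stable disease from week 23 (SAP 2.7.1), and the PFS rule for missed scans adds twice the window (SAP 2.7.3). Leaving BOR = PD without such an allowance looks like an oversight.

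**Working it through.** **Inputs**
- PD limit: 12 weeks from start of treatment, 12 × 7 = 84 days (Appendix 5, 3.1).
- Scan interval behind that limit: 6 weeks (Appendix 5, 3.1).
- Scan interval in this trial: 12 weeks, window 7 days either way (protocol 7.2.1.1).
- Day count for time-to-event variables: end date minus start date plus 1 (Appendix 5, 4.5.1). SAP 2.1.1 defines study day the same way for dates on or after treatment start.

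**Step 1: the appendix's own window figure.** 6 weeks − 7 days = 42 − 7 = 35 days = 5 weeks. This reproduces the SD example.

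**Step 2: the schedule the default assumes.** With 6-week scans and a 7-day window, the first scan falls no later than 42 + 7 = 49 days. That is well inside 84, so progression at an in-window first scan is always PD.

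**Step 3: this trial's schedule.** The first scan may fall from 84 − 7 = 77 to 84 + 7 = 91 elapsed days, which is 15 allowed days. For a patient with no earlier SD or response:

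| Convention | Elapsed days giving PD | Elapsed days giving Unknown |
|---|---|---|
| Elapsed days | 77–84 (8 days) | 85–91 (7 days) |
| End − start + 1 | 77–83 (7 days) | 84–91 (8 days) |

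Under the second convention a scan exactly 84 days after start counts as day 85, so even a scan on the target day fails the limit. SAP 2.1.1 itself gives Cycle 4 Day 1 a target of day 85. Appendix 5 does not say which convention applies to the BOR limits.

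**Step 4: the limit with the window added.** 12 weeks + 7 days = 84 + 7 = 91 days = 13 weeks. In elapsed days, none of the 15 allowed days gives Unknown. If days are counted as end − start + 1, the last allowed day counts as 92. A limit coded as 91 would still miss that day, so it must be written as study day 92.

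**Step 5: what changes downstream.**
- ORR: Unknown BOR counts as failure (SAP 2.7.3), as does PD. No change.
- CBR: needs CR, PR, or SD or Non-CR/Non-PD lasting about 24 weeks. Neither PD nor Unknown qualifies. No change.
- PFS and the 6-month primary endpoint: both use the progression itself, not the BOR category. No change.

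**The case against.** The strongest objection is that no planned endpoint moves. SAP 2.7.2 plans ORR and CBR with exact intervals and does not list a table splitting PD from Unknown; BOR summary tables appear only in the generic text of Appendix 5, section 3.2.9. This stands, and it limits the point to a category label. The label is still derived by a stated rule, and the rule gives the wrong answer for a documented, on-schedule progression.

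A second objection is that the appendix allows windows to be taken into account. It does, but as an option, and it requires a different PD period to be written in the protocol. With nothing written, 12 weeks remains. The SAP 2.7.3 sentence that spares patients from Unknown when progression is reported covers only those with no valid post-baseline assessment.

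Third, several rules bring PD dates forward. A PD assessment is dated by its earliest measurement (Appendix 5, 3.2.8; SAP 5.1.2.1). Suspected progression calls for prompt imaging (protocol 7.2.1.1). A scan is due at end of treatment if the last is more than 30 days old (protocol 7.1.5). All of this stands and lowers the number affected.

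A reader might go further and apply 7/15 to an assumed early-progression rate to obtain patients per cohort. The documents do not support that. They give no distribution of scan dates, and 7/15 is a share of allowed days. The planning rate of 0.45 belongs to an endpoint that also counts deaths and study discontinuations as failures, so it does not yield a rate of progression at the first scan.

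**Conclusion.** The point holds. As written, the BOR rule classes progression at a compliant first scan on elapsed days 85 to 91 as Unknown when there is no earlier SD or response, and also on day 84 under the end − start + 1 count. The effect is confined to the division between PD and Unknown within BOR. The number of patients affected cannot be computed from the documents. The conclusion assumes that the appendix default is applied as written; the separate programming specification mentioned in SAP 5.1 was not available to check.

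Three stronger readings are not supported:
- **That the trial would hide primary resistance.** PFS counts documented progression at its actual date, apart from events after two or more missed assessments, and SAP 2.7.2 plans Kaplan-Meier curves and quartiles by cohort.
- **That the limit should be 25 weeks, to keep a span of two scans.** The appendix never states a two-scan principle. It calls the category early progression, so Unknown is a defensible label for first PD at week 24 after an unevaluable week-12 scan. What is missing is a statement of which label applies.
- **That the SD minimum must rise to 11 weeks.** That would not cure this problem, and it could move some SD patients to Unknown.

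**What to change.** State in protocol 10.5.1.3 and SAP 2.7.1 that BOR = PD applies to progression up to 13 weeks after start of treatment, that is 12 weeks plus the 7-day window. Give the limit in days with its convention: 91 elapsed days, or study day 92 if counted as end − start + 1. Add one sentence saying how a first documented PD after a missed or unevaluable week-12 scan is classified; a 13-week limit alone leaves such a patient as Unknown when PD is found at week 24.

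The cost is a sentence or two and one programming constant. No endpoint estimate or test changes. If BOR outputs already exist, re-deriving the category or adding a footnote is enough.
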